# 9.2. Identity of Investigational Products

The following treatments will be used during the study:

- CAM2038 q1w, 50 mg/mL: 24 and 32 mg (BPN base), 0.48 mL and 0.64 mL SC injection. Subcutaneous injections will be performed in the upper buttocks rotating between right and left buttocks.
- Hydromorphone, 10 mg/mL (Dilaudid HP®): 6 and 18 mg for IM administration. Intramuscular injections will be performed in the deltoid muscle.
- Morphine IR 30 mg tablet for oral administration.

CAM2038 q1w will be supplied as pre-filled syringe with safety device and plunger containing the following: BPN, soybean phosphatidylcholine, glycerol dioleate, and ethanol. More information regarding the CAM2038 q1w can be found in the Study MOP.

Dilaudid HP® will be supplied as single dose vials for IM administration. Each 1 mL of sterile solution contains 10 mg/mL mg hydromorphone hydrochloride with 0.2% sodium citrate and 0.2% citric acid solution.

- For the hydromorphone 18 mg dose, 1.8 mL of this solution will be used.
- Hydromorphone 6 mg dose will be a combination of 0.6 mL Dilaudid HP solution + 1.2 mL ½ NS sodium and water for a total injection volume of 1.8 mL.
- Hydromorphone 0 mg (placebo) will be administered using 1.8 mL of a solution of 0.45% sodium and water (1/2 NS).

Version: 2.0, 17NOV2015 Page 49 of 99

Morphine Sulfate will be supplied as 30 mg tablets.

Each container of study drug will be clearly labeled with study-specific information meeting all the applicable regulatory requirements.

#### 9.2.1. Handling, Storage, and Accountability

All study drugs will be transported, received, stored, and handled strictly in accordance with the container or product label, the instructions provided to the research site, and applicable regulations.

CAM2038 products must be stored according to the requirements outlined in the Study MOP. Storage requirements for hydromorphone are provided in the product label (a copy is provided in the Study MOP).

Detailed drug accountability records must be maintained, including the dates shipments are received, the quantity of material received, the dates dispensed, the running inventory, and the unused quantities returned to the Sponsor's drug supply vendor at the end of the trial. All unused supplies will be checked against the drug accountability records during the study and/or at the end of the study. Additional details are provided in the Study MOP.

Buprenorphine (Schedule III), morphine sulfate and hydromorphone (Schedule II) are controlled substances and study drugs must be handled and stored strictly in accordance with restrictions related to controlled substances. Study drugs must be kept securely locked with access limited to appropriate study personnel, according to applicable regulations.

#### 9.2.2. Dispensing and Administration

Only eligible subjects participating in the study will receive the study drug. Only authorized research site staff may administer the study drugs. Once dispensed, study drug may not be relabeled or reassigned for use by other subjects.

CAM2038 q1w SC injections, hydromorphone IM injections, and IR morphine 30 mg tablets will be administered by designated healthcare professional(s) at the CRU. Detailed instructions for use will be provided in the Study MOP.

Investigators will be instructed to treat AEs as they would usually, including pharmacological interventions. Any pharmacological interventions provided by the Investigators will be recorded, along with the reasons for determining the need for these interventions. Further instructions on handling precipitated withdrawal is addressed in Section 10.6.

# 9.3. Method of Assigning Subjects to Treatment Groups

Subjects who have provided written informed consent will be assigned a unique number in the screening process. This number will be used to identify the subject throughout the study.

Subjects will be randomized in a 1:1 ratio to 1 of 2 groups (CAM2038 q1w at doses of 24 mg or 32 mg) stratified by gender. If a subject discontinues from the study, that subject may be replaced at the discretion of the Sponsor. The replacement subject will receive the same treatment

Version: 2.0, 17NOV2015 Page 50 of 99

(CAM2038 q1w) and will follow the same treatment sequence in the Hydromorphone Challenge Sessions as the original subject in the Treatment Phase.

For the Hydromorphone Challenge Sessions, subjects will be randomized in a 1:1:1:1:1 ratio to 1 of 6 treatment sequences according to two 3 × 3 William squares. The following treatment sequences will be used: ABC, ACB, BAC, BCA, CAB, and CBA, where A, B, and C are IM hydromorphone doses of 0 mg (placebo), 6 mg, and 18 mg, respectively

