# 8.4. Removal of Subjects from Therapy or Assessment

A subject is free to withdraw his/her consent and discontinue participation in the study at any time for any reason. A subject's participation must therefore be terminated immediately upon his/her request, and the reason(s) for discontinuation appropriately documented.

A subject must be discontinued from the study for any of the following reasons:

- Safety reasons, including AEs or significant concomitant illness, injury, or urgent surgeries/procedures that would, in the judgment of the Investigator, affect assessments of clinical status to a significant extent, require discontinuation of study drug, or both
- At the request of the Sponsor, regulatory agency, or Institutional Review Board (IRB)
- Subject is lost to follow-up
- Subject treatment allocation is unblinded during the Treatment Phase (i.e., individual code break; Section 9.6)
- Death of subject

A subject may also be discontinued from the study, at the discretion of the Investigator and/or Sponsor, for any of the following reasons:

- Subject refuses or is unable to adhere to the study protocol
- Protocol violation
- Pregnancy
- Requirement for continual use of opioid analgesics >7 days or requirement for general anesthesia for surgery

The Investigator must maintain a record of all subjects who discontinue from the study prior to completion; the reason(s) for study discontinuation will be documented. In the event that a subject chooses to withdraw from the study, the Investigator should make a reasonable attempt to obtain and record the reason(s) for withdrawal, if possible, although the subject is not obligated to provide such a reason.

All efforts should be made by the Investigator to continue collection of safety assessments at the protocol-defined intervals, including concomitant medications and AEs in subjects that discontinue study drugs, unless the subject withdraws his/her consent at the time of early discontinuation. The Investigator should also ask the subject to complete Follow-up phone-call, provided that the subject has not withdrawn consent. If a subject refuses to complete Early Termination procedures and/or Follow-up, this information will be recorded.

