# 9.6. Blinding

In order to reduce the potential for bias in the study, Hydromorphone Challenge Session treatment sequences and CAM2038 q1w treatment group assignments will be double-blinded. The subjects will not be aware of the treatment group assignments. The randomization scheme will be provided to the site's unblinded personnel for preparation of the individual subject doses. If necessary, personnel from the bioanalytical laboratory will have access to the randomization scheme.

Upon completion of each double-blind, Qualification/Baseline Hydromorphone Challenge Session cohort of subjects, the randomization codes for the completed subjects will be unblinded to the designated personnel, and the eligibility of subjects to participate in the Treatment Phase will be assessed as described in Section 8.3. In order to maintain the blind, unblinded staff not otherwise involved in the study will prepare the hydromorphone doses so that they are volume-matched (1.8 mL, See Section 9.2).

There is a slight difference in fill volume between the different doses of CAM2038 q1w; however, the viscosity is the same. In order to maintain the blind given the differences in color fill volume, the following procedures will be implemented:

- The Injecting staff member and any other staff involved in the injection process will not participate in subject evaluations, nor discuss any information regarding the injections with the subjects or other study staff.
- To keep the subjects blinded, appropriate steps will be taken to ensure that the subject is unable to view the syringe at any time.

Under normal circumstances, the blind will not be broken until all subjects have completed treatment. In case of emergency, and only if the information is required by the Investigator to manage a subject's medical condition, a subject's treatment may be unblinded at the site with the approval of the Sponsor. Whenever a treatment is prematurely unblinded, the reason, date and time of the unblinding, and the individual who broke the blind must be documented. Individual code breaks will result in withdrawal of the subject from the study.

Version: 2.0, 17NOV2015 Page 52 of 99

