# 12.1. Sample Size Determination

A sample size of 24 subjects will provide 90% power for the CAM2038 32 mg to demonstrate no significant difference in the mean  $E_{max}$  score of the Drug Liking VAS comparing to 0 mg hydromorphone at a two-sided 0.05 significance level with a non-significant difference cutoff at  $\leq 11$  points. In the sample size calculation it was assumed that the true difference was less than or equal to 1.5 and the standard deviation was 9.8.

An additional group of 24 subjects will be enrolled to CAM2038 24 mg group. This sample size will provide approximately 83% power for the CAM2038 24 mg to demonstrate no significant difference in the mean  $E_{max}$  score of the Drug Liking VAS comparing to 0 mg hydromorphone at a two-sided 0.05 significance level with a non-significant difference cutoff at  $\leq$  11 points. In the sample size calculation it was assumed that the true difference was less than or equal to 2.5 and the standard deviation was 9.8.

The plan will be to enroll a sufficient number of subjects to ensure that at least 48 subjects complete the study (24 subjects per treatment group) by over-enrollment as needed and replacement of subjects for those who drop out.

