9.6 POWER AND SAMPLE SIZE JUSTIFICATION

A sample size of 24 subjects will provide 90% power for the CAM2038 32 mg to demonstrate no significant difference in the mean E_{\max} score of the Drug Liking VAS comparing to 0 mg hydromorphone at a two-sided 0.05 significance level with a non-significant difference cutoff at ≤ 11 points. In the sample size calculation it was assumed that the true difference was less than or equal to 1.5 and the standard deviation was 9.8.

Additional 24 subjects will be enrolled to CAM2038 24 mg group. This sample size will provide approximately 83% power for the CAM2038 24 mg to demonstrate no significant difference in the mean E_{\max} score of the Drug Liking VAS comparing to 0 mg hydromorphone at a two-sided 0.05 significance level with a non-significant difference cutoff at ≤ 11 points. In the sample size calculation it was assumed that the true difference was less than or equal to 2.5 and the standard deviation was 9.8.

The plan will be to enroll a sufficient number of subjects to ensure that approximately 48 subjects complete the study (24 subjects per treatment group) by over-enrollment as needed.

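### The replacement rule in Protocol 9.3 can reuse an allocation that site staff already know, because subjects withdrawn for a code break are not exempt from it

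*Protocol*

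**What the plan says.** Protocol 9.3 sets a general trigger: "If a subject discontinues from the study, that subject may be replaced at the discretion of the Sponsor". It then fixes the allocation. "The replacement subject will receive the same treatment" (the CAM2038 dose), and the new subject "will follow the same treatment sequence in the Hydromorphone Challenge Sessions as the original subject in the Treatment Phase". The Synopsis and Protocol 8 add that replacement needs the investigator's agreement.

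Protocol 8.4 includes this among the reasons for compulsory discontinuation: "Subject treatment allocation is unblinded during the Treatment Phase". Protocol 9.6 repeats the rule: "Individual code breaks will result in withdrawal of the subject from the study". Under 9.6 the code is broken at the site, in an emergency, with the sponsor's approval, because the investigator needs the information. The same section states that both the hydromorphone sequences and the CAM2038 groups are double-blind.

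Replacement is part of how the trial reaches its number. Protocol 12.1 plans for at least 48 completers "by over-enrollment as needed and replacement of subjects for those who drop out". The SAP has no rule for how a replacement is allocated.

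**The concern.** Each rule is reasonable alone, but together they leave a gap. A code break forces withdrawal, withdrawal makes the subject replaceable, and replacement reuses the allocation that has just been disclosed. No section exempts this case, sends the replacement back to the randomisation list, or keeps from the site which subject is being replaced.

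The staff blind matters here even though Drug Liking is self-rated. Protocol 7.2 relies on subjects and staff both being unaware of the hydromorphone dose to limit expectancy effects. Under Protocol 10.3, staff watch how subjects complete the scales and may retrain them. Under 7.1.4, they decide whether it is safe to give the next challenge dose. Entry to the Treatment Phase also rests partly on judgement: Protocol 8.3 asks whether overall responses are acceptable and whether behaviour suggests that the subject will finish. An investigator who has seen the code could make that judgement knowing what the replacement will receive. The replacement, if it completes, then enters the Completer Population, on which the primary analysis is run.

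**Working it through.** **1. The chain of rules.** A code break leads to withdrawal (8.4, 9.6). Withdrawal makes the subject replaceable at the sponsor's discretion (9.3), with the investigator's agreement (8). The replacement inherits dose and sequence (9.3). The sponsor and the site investigator take part in both the break and the replacement. No provision interrupts the chain.

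**2. What the site could know.** There are two CAM2038 doses at 1:1 and six hydromorphone sequences in equal ratio (9.3). Taking one sequence per subject, a blinded observer has probability 1/2 x 1/6 = 1/12 = 8.3% of naming the pair. For someone who saw a break that covered both items, the probability is 1. The Treatment Phase has 4 sessions x 3 days = 12 challenge days. One such subject is 1/24 = 4.2% of a group.

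**3. The plan's own power.** Inputs from Protocol 12.1 and SAP 9.6: 24 per group, margin 11, SD 9.8, two-sided 0.05 (0.025 on the upper bound), true difference 1.5 (32 mg) or 2.5 (24 mg). Treating the two hydromorphone conditions as independent:

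- Standard error = 9.8 x sqrt(2/24) = 2.829, with 46 degrees of freedom.
- 32 mg: (11 - 1.5)/2.829 = 3.36, noncentral t power 90.8% (stated: 90%).
- 24 mg: (11 - 2.5)/2.829 = 3.00, noncentral t power 83.7% (stated: about 83%).

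The stated figures reproduce, and this point does not dispute them.

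**4. Possible size of the effect.** The documents give neither a code-break rate nor a size of bias, so both are assumed. Let k be the number of replacements with a known allocation among 24 completers. Suppose the knowledge lowers the active-minus-placebo difference by b = 5 to 10 points in those subjects. The shift in the group mean is k x b/24. The one-sided error at a true difference of 11 is the upper tail of a noncentral t with 46 degrees of freedom and noncentrality shift/2.829.

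| k | Share of group | Shift (b = 5 to 10) | One-sided error (nominal 0.025) |
|---|---|---|---|
| 1 | 4.2% | 0.21 to 0.42 | 0.030 to 0.035 |
| 2 | 8.3% | 0.42 to 0.83 | 0.035 to 0.047 |
| 6 | 25% | 1.25 to 2.50 | 0.063 to 0.137 |

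If the bias ran the other way, one case would cut power from 90.8% to 89.5-88.2% (32 mg) and from 83.7% to 81.8-79.9% (24 mg). These figures use the variance from the sample-size calculation, not the SAP's mixed model, so they indicate order of magnitude only.

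**The case against.** The strongest reply is that the route needs several steps which the documents do not state. The trial is multi-site, and nothing says that a replacement enrols where the original did. Nothing says that evaluators learn whose place a new subject fills. A break is reserved for emergencies. The sponsor can decline to replace. Protocol 9.6 speaks only of a subject's treatment, so a break may not show the hydromorphone order. Separate unblinded staff prepare the hydromorphone doses, injection volumes are matched at 1.8 mL, and the subject gives the ratings without having seen the code. All of this stands. It makes the case rare and the leak indirect, but none of it is a rule that prevents the case.

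The reply also disposes of several stronger readings that a reader might infer:

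- **That no replacement is randomised or blinded.** An inherited place came from the random list. While the original's code is sealed, the allocation stays concealed and does not depend on who fills it. The Summary of Changes gives balance and adequate numbers in each group as the reason for the rule. Taking the next list entry for every replacement would be a design preference.
- **That 5 to 10 of 48 completers are affected.** This needs an assumed 10-20% dropout (48 x 0.10 = 4.8; 48 x 0.20 = 9.6), and it counts concealed replacements. It says nothing about code breaks.
- **That gender stratification is lost in a way that matters.** Protocol 9.3 does not require a replacement of the same gender. However, SAP 9.1.2 analyses each CAM2038 group separately, with within-subject contrasts and no gender term, and the ordered tests in SAP 9.4 do not compare the two CAM2038 doses.
- **That SAP 9.6 shows copying to be unnecessary.** It mentions over-enrolment only, but it does not exclude replacement, and Protocol 12.1 names both.

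**Conclusion.** The gap is real, narrow and minor. As written, 9.3 permits reuse of an allocation disclosed at the site, which conflicts with the double-blind standard in 9.6. It has consequences only if a code-broken subject is replaced, at the same site, with the link known to staff, after a break that showed dose and sequence. Staff who saw the code could then know the allocation before entry and on up to 12 challenge days. The hydromorphone order matters more than the CAM2038 dose, because the primary contrast is within subject.

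One case is 4.2% of a group and would have a small effect: a one-sided error of about 0.030-0.035 under an assumed bias of 5 to 10 points. The larger figures in the table need several such replacements in one group of 24, and the documents give no basis for expecting that. The case for acting is that the repair costs almost nothing.

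**What to change.** Add to Protocol 9.3:

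> The allocation of a subject whose code was broken will not be reused; any replacement for that subject is assigned the next unused entry for his or her gender stratum and the next unused hydromorphone sequence on the centrally held list. For all other replacements, the link between original and replacement is held centrally and not disclosed to blinded site staff.

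The cost is two sentences, a few spare entries on the list, and someone outside the blinded site team to hold the link. Like-for-like replacement continues in every other case. The sample size and the analysis model do not change. The downside is that group or sequence counts may differ by one or two from exact balance.

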#### 9.4. Selection of Doses

The full mu opioid agonist hydromorphone will be used for the opioid challenge sessions. Hydromorphone has been commonly employed for this purpose as it has favorable pharmacokinetics and is similar to heroin in its time course and pharmacodynamic profile. It has a high abuse liability and obviates the challenges of using a Schedule I agent (i.e., heroin). Numerous opioid challenge studies have used hydromorphone specifically to examine the ability of putative opioid dependence treatments to produce opioid blockade (Walsh et al., 1995; Bickel et al., 1988; Strain et al., 1997; Sobel et al., 2004; Ciraulo et al., 2006; Walsh et al., 2006; Lanier et al., 2010) so there is a strong precedent for the choice of this compound.

Initial parenteral doses of hydromorphone for analgesia are 1 to 2 mg subcutaneously or IM every 2 to 3 hours PRN (Handelsman et al., 1987; Hydromorphone, 1984). However, supratherapeutic doses are needed for challenge studies in opioid abusers. Typically, a lower range of supratherapeutic doses can be employed in opioid abusing individuals without physical dependence and still produce robust dose-related effects. However, higher supratherapeutic doses are needed when investigating responses in active opioid abusers with physical dependence (and hence, higher levels of tolerance). Studies that have examined the ability of BPN maintenance treatment to produce blockade of hydromorphone effect have varied. For example, one openlabel trial of a depot BPN formulation examined hydromorphone doses of 0 mg and 3 mg (on the low end), but this product produced BPN plasma concentrations of under 2 ng/mL (a target range generally accepted as the lower therapeutic concentration for blockade, but effective for withdrawal suppression). Other studies have employed higher hydromorphone doses during BPN and methadone maintenance treatment ranging between 10 mg to 18 mg. In one early study, BPN SL solution (estimated to have approximately 30% higher bioavailability over the currently marketed tablets) (Handelsman et al., 1987; Hydromorphone, 1984) examined blockade with BPN maintenance doses ranging from 2 mg to 16 mg/day using a cumulative SC hydromorphone dosing procedure of 0 mg, 6 mg, and 12 mg, for a total challenge dose of 18 mg. A recent study examining blockade with another sustained-release BPN product (RBP 6000, Clinical Trials.gov, NCT02044094) examined single acute doses of 0 mg, 6 mg and 18 mg. Based upon prior studies of methadone and BPN maintenance, the proposed doses are appropriate for opioid challenge studies, should be safely tolerated during the Qualification Phase and should reflect attenuated responses after stabilization on BPN.

CAM20138 q1w doses of 24 mg and 32 mg were selected to represent a range of therapeutic doses that are being evaluated in Phase III efficacy studies.

Version: 2.0, 17NOV2015 Page 51 of 99

# 9.5. Selection and Timing of Dose

During the Treatment Phase, Hydromorphone Challenge Session doses will be administered as single IM doses once daily over 3 days, with each daily dose administered at approximately 9:00 am. CAM2038 q1w SC injections will be administered on Days 0 and 7 at approximately 9:00 am. The drug administration time should remain consistent (±10 minutes), if possible, on all dosing days (CAM2038q q1w and hydromorphone) of the Treatment Phase.

All subjects will receive standard meals at specified times. Dietary restrictions are described in Section 8.5.

# 9.6. Blinding

In order to reduce the potential for bias in the study, Hydromorphone Challenge Session treatment sequences and CAM2038 q1w treatment group assignments will be double-blinded. The subjects will not be aware of the treatment group assignments. The randomization scheme will be provided to the site's unblinded personnel for preparation of the individual subject doses. If necessary, personnel from the bioanalytical laboratory will have access to the randomization scheme.

Upon completion of each double-blind, Qualification/Baseline Hydromorphone Challenge Session cohort of subjects, the randomization codes for the completed subjects will be unblinded to the designated personnel, and the eligibility of subjects to participate in the Treatment Phase will be assessed as described in Section 8.3. In order to maintain the blind, unblinded staff not otherwise involved in the study will prepare the hydromorphone doses so that they are volume-matched (1.8 mL, See Section 9.2).

There is a slight difference in fill volume between the different doses of CAM2038 q1w; however, the viscosity is the same. In order to maintain the blind given the differences in color fill volume, the following procedures will be implemented:

- The Injecting staff member and any other staff involved in the injection process will not participate in subject evaluations, nor discuss any information regarding the injections with the subjects or other study staff.
- To keep the subjects blinded, appropriate steps will be taken to ensure that the subject is unable to view the syringe at any time.

Under normal circumstances, the blind will not be broken until all subjects have completed treatment. In case of emergency, and only if the information is required by the Investigator to manage a subject's medical condition, a subject's treatment may be unblinded at the site with the approval of the Sponsor. Whenever a treatment is prematurely unblinded, the reason, date and time of the unblinding, and the individual who broke the blind must be documented. Individual code breaks will result in withdrawal of the subject from the study.

Version: 2.0, 17NOV2015 Page 52 of 99

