# 10.6. Additional Safety Measures and Withdrawal

#### 10.6.1. Opioid Effects

Buprenorphine and hydromorphone can produce the typical side effect profile of mu opioid agonists, and these may include nausea, vomiting, headache, dry mouth, itchiness, drowsiness, sweating, dizziness, stimulation, somnolence, lightheadedness, restlessness, a feeling of well-being, talkativeness, urinary retention and constipation. More serious side effects may include allergic reaction and respiratory depression. However, subjects will be opioid-dependent and, thus, familiar with these common side effects, and not likely to experience the severe side effects such as allergic reaction.

Physiological and behavioral effects, as well as the emergence of possible side effects, will be monitored daily during Hydromorphone Challenge Sessions. Subjects who exhibit hypersensitivity (i.e., experience a SAE) following administration of any of the drugs will be excluded from further research participation. Heart rate, blood pressure, oxygen saturation and respiratory rate will be monitored frequently throughout sessions. However, if a subject experiences an allergic reaction, diphenhydramine will be available for oral administration.

While the risk of significant respiratory depression may be decreased in opioid-dependent individuals (due to greater tolerance), standardized criteria for nursing staff and research personnel will be employed during the monitoring of individuals. If respiratory rate drops below 12 breaths/min accompanied by sedation, subjects will be prompted verbally to breathe. This approach of physical and verbal stimulation is often sufficient to prompt breathing and restore a normal respiratory rate. Subjects will be monitored carefully with a watch-and-wait approach and will be accompanied continuously by nursing personnel and evaluated by the staff physician. If clinical evaluation determines that a subject's level of sedation is increasing, naloxone will be promptly administered parenterally to produce immediate reversal of the hydromorphone effects. Naltrexone will also be available if longer blockade is necessary.

The study will be conducted in CRUs with trained nursing staff available on site. A crash-cart with naloxone will be on site as well. Emergency response will be available by a physician codeteam if needed.

Version: 2.0, 17NOV2015 Page 65 of 99

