# 13.3. Study and Site Closure

Upon completion of the study, all study data will be provided to the Sponsor following review of site study records for completeness, and data clarifications and resolutions. Accounting, reconciliation, and final disposition of used and unused study drugs, treatment codes, and emergency code break envelopes will be performed, as applicable.

In addition, the Sponsor reserves the right to temporarily suspend or prematurely discontinue this study at any time and for any reason. If such action is taken, the Sponsor will discuss this with

Version: 2.0, 17NOV2015 Page 76 of 99

the Investigator (including the reasons for taking such action) at that time. The Sponsor will promptly inform any other investigators and/or institutions conducting the study, if the study is suspended or terminated for safety reasons and will inform the regulatory authorities of the suspension or termination of the study and the reason(s) for the action. If required by applicable regulations, the Investigator will inform the IRB promptly and provide the study subjects with the reason for the suspension or termination. If the study is prematurely discontinued, all study data will be returned to the Sponsor.

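### Protocol 9.6 makes an emergency code break at the site wait for Sponsor approval, with no time limit or fallback, although the code is already held on site.

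*Protocol*

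**What the plan says.** Protocol 9.6 blinds two things: "Hydromorphone Challenge Session treatment sequences and CAM2038 q1w treatment group assignments will be double-blinded". The rule on code breaks therefore covers the daily hydromorphone dose as well as the weekly CAM2038 dose.

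The rule opens with a narrow condition: "In case of emergency, and only if the information is required by the Investigator to manage a subject's medical condition". It then continues that the subject's "treatment may be unblinded at the site with the approval of the Sponsor". The reason, date, time and person must be documented. The consequence is also fixed: "Individual code breaks will result in withdrawal of the subject from the study". Section 8.4 agrees, listing unblinding during the Treatment Phase among the reasons for mandatory discontinuation.

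On who holds the code, 9.6 says: "The randomization scheme will be provided to the site's unblinded personnel for preparation of the individual subject doses". Section 13.3 lists, among the items to be reconciled when the study closes, "treatment codes, and emergency code break envelopes will be performed, as applicable". That is the only mention of envelopes.

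The SAP has no emergency procedure. Its sections 3.0 and 6.3 mention unblinding only in relation to finalizing the plan and locking the database.

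**The concern.** The first two conditions in 9.6 already establish that there is an emergency and that the treating Investigator needs the code. Making the break also depend on the agreement of a party who is not at the bedside puts a step of open-ended length into an emergency path. If the Sponsor cannot be reached, the text gives the Investigator no permitted way to obtain the code.

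What is at stake is how quickly the Investigator gets information already judged necessary. The population gives the question some weight: Protocol 9.4 describes the challenge doses as supratherapeutic, and 10.6.1 names respiratory depression among the more serious possible effects.

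**Working it through.** The point contains no plan figure to reproduce and needs no calculation for the defect itself. The check is a reading of every place that bears on it.

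1. **Is approval a precondition or a courtesy?** A precondition. The clause in 9.6 has no qualifier such as *where possible* and no route for approval after the event.

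2. **Does any other section relax it?** None does.
   - 8.4 adds only the consequence of a code break.
   - 9.7 governs concomitant medication, not codes.
   - 10.6.1 governs emergency care and does not mention the code.
   - 13.3 deals with reconciliation at closure.
   - SAP 3.0 and 6.3 deal with unblinding for analysis.
   - The 24-hour limit in 10.4.1.2.1 is for the site to report a serious adverse event. It sets no time for a Sponsor reply.

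3. **Does the Protocol treat similar steps the same way?** It is more flexible elsewhere. In 9.7, approval by the Medical Monitor of a medication outside Table 5 is to be sought beforehand whenever possible. In 13.6, prior ethics approval of an amendment is waived where an immediate hazard to the subject must be removed. Neither provision applies to code breaks, but each shows the kind of exception that 9.6 lacks.

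4. **Is the code physically out of reach?** No. The site's unblinded personnel have the randomization scheme. No text allows them to release it to the Investigator without the Sponsor's approval.

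5. **Do the envelopes solve the problem?** The documents do not say. Section 13.3 mentions them only for accounting and only as applicable. It does not establish that they are used in this trial, who keeps them, or who may open them.

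6. **Does emergency treatment wait for the code?** Not under 10.6.1. There the response follows clinical evaluation: if sedation is judged to be increasing, "naloxone will be promptly administered parenterally to produce immediate reversal of the hydromorphone effects". Knowing the assigned dose is not a condition.

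7. **What would an additional code break cost the analysis?** The subject is withdrawn (8.4, 9.6). The Completer Population consists of subjects who complete Day 14 and is the basis of the primary analysis (12.2), so the subject leaves that analysis. With 24 completers planned per group (12.1), one lost subject is 1/24 = 4.2% of a group unless replaced. Section 9.3 permits replacement at the Sponsor's discretion, and 12.1 plans over-enrollment and replacement to reach 48.

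**The case against.** The strongest reply is that no harm is shown. Subjects are inpatients, monitored from before each challenge dose until 5 hours after it, with trained nursing staff, naloxone and an emergency team available. Staff know that the agent is hydromorphone at 0, 6 or 18 mg, so the worst case is known without a code break. This stands as a limit on severity. A reader might infer from the clause that reversal of an opioid emergency is held up, and 10.6.1 does not support that. It does not defend the clause, however, because 9.6 applies only where the Investigator does need the code.

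A second reply is that approval has a purpose. It is tempting to say that the step adds nothing beyond documentation, but that goes too far: a code break costs a completer, so a check on necessity has some value. That value is limited, since the documentation duty and automatic withdrawal already discourage casual breaks.

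Third, contact routes and response times may be set out in the Manual of Procedures or the SAE Reporting and Management Plan, which are not available here. This is fair, and the absence of a time limit is established only for the Protocol and SAP. But 9.6 does not refer to either document on unblinding, and a contact list would not remove the precondition.

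Finally, a reader might take 13.3 to contradict 9.6. It does not. The two sections are unreconciled: one names emergency envelopes, and neither says how they relate to the approval rule.

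**Conclusion.** The point holds as a defect in a stated rule. Under 9.6 the Investigator may not obtain the code before the Sponsor agrees, even when the Protocol's own emergency condition is met, and the Protocol and SAP set no limit on the wait and no fallback.

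The size of the delay cannot be given. It is a delay of information, it may be short, and the documents state neither a Sponsor response time nor an expected rate of emergencies or code breaks. Counting the blinded injections, as a reader might do to gauge the scale, would measure routine dosing and not this problem.

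The conclusion assumes that no unseen operational document overrides 9.6. It should be corrected because the remedy is small and the clause governs emergencies. The independence of first-line reversal from the code keeps it from being more serious.

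**What to change.** In 9.6, replace prior approval with Investigator authority under the existing condition. Wording along these lines would do:

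> When the emergency condition above is met, the Investigator may obtain the subject's code at the site. The Sponsor is contacted beforehand where this is possible and is otherwise notified promptly afterwards. The reason, date, time and person are documented.

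Then reconcile 9.6 with 13.3. If code break envelopes are used, say who holds them and who may open them. If they are not used, delete the reference and say how the Investigator obtains the code from the unblinded site personnel.

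This changes only who may authorize disclosure of a code. It alters no dose, rescue treatment or stopping rule.

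The editing cost is a sentence in 9.6 and a line on the envelopes. The downside is possibly a few more code breaks, each removing a subject from the study and from the Completer primary analysis and possibly requiring a replacement.
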